To determine the effect of consumption of milk beverages enriched with Lactobacillus rhamnosus y Bifidobacterium longum in dental plaque index.	The comparison of dental plaque index during the intake of milk without probiotic versus during the intake of milk with probiotic, show us if Lactobacillus rhamnosus and Bifidobacterium longum reduce the formation of dental plaque.	Other studies, showed that some probiotics reduce the dental plaque.

8. Study Design

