7.1 Hypothesis

1. The commercial milk beverages enriched with *Lactobacillus rhamnosus* and *Bifidobacterium longum* reduce the demineralization of caries lesion (ICDAS 1-4).
2. The commercial milk beverages enriched with *Lactobacillus rhamnosus* and *Bifidobacterium longum* reduce the change of salivary pH after a rinse with sugar.
3. The commercial milk beverages enriched with *Lactobacillus rhamnosus* and *Bifidobacterium longum* reduce the quantification of mutans streptococci in saliva.
4. The commercial milk beverages enriched with *Lactobacillus rhamnosus* and *Bifidobacterium longum* reduce the dental plaque.

7.2 Study design: Nonrandomized comparison, single group assignment, controlled before and after study.

7.3 Arm treatment information:

- A. Experimental: Commercial Cow Milk with Probiotic. 200 ml of commercial nutritive milk fortified with probiotic *Lactobacillus rhamnosus* and *Bifidobacterium longum* once a day.
- B. Placebo comparator: Commercial Dairy Cow Milk 200 ml of commercial nutritive milk without probiotic, once a day.

7.4 Dosing and administration:

Experimental: 200 ml of commercial nutritive milk fortified with probiotic *Lactobacillus rhamnosus* and *Bifidobacterium longum* (Nan Pro3, Nestlé) once a day.

Placebo comparator: 200 ml of commercial nutritive milk without probiotic (Klim Fortificada Nestlé), once a day.

7.5 Study intervention duration:

3 months intake the placebo comparator, and 3 months intake the experimental treatment.

7.6 Sites:

Kindergarten in Villavicencio, Colombia

Kindergarten in Pasto, Colombia

7.7 Phase of the trial:

1. Invitation to participate in the trial: at the kinder garden during a meeting, the researchers invite parents to participate.
2. To request the informed consent of the parents of the children.
3. Diagnosis, selection, and collection of samples. Each child will be informed of the process in a simple way.

First Day:

- 3.1 First selection: the dentist checks up the oral health condition. Children without caries or with advanced caries will not continue in the process. Children who enter the criteria continue in the process.
- 3.2 Second selection: Clinical assessment of demineralization with Diagnodent, after of dental prophylaxis. The children with measure upper to 7, are included.
- 3.3 ICDAS: dentist with calibration in ICDAS take this measure.

Second day:

- 3.4 Index dental plaque Sillness and Löe.

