6. INTERVENTION

Children were given 200 mL of milk with after the breakfast every day, for five days a week. First, the children will drink milk without probiotic, during the 3-months period. And then the children drink milk with probiotic during the 3-months period (*L. rhamnosus* and *B. longum*). The nursery school staff prepared the commercial milk with researcher supervision. The milk will be prepared with safe water (packaged water).

6. After the intervention with each milk, the next outcome measures:

6.1 Index dental plaque Sillness and Löe.

6.2 Collection of saliva: Each child will accumulate saliva and then collect it in sterile containers (approximately 1.5-2 ml).

6.3 1 ml of saliva with glycerol (10%) will be frozen (-20°C) in microcentrifuge tubes (1.5ml). This sample is for microbiological analysis of *S. mutans*).

6.4 With the other 1ml is to determine the pH. The Salivary pH will be determined with pHmeter Fisherbrand Accumet Portable AP110.6.5 Rinse with 10% sugar solution. The children will make a mouthwash with sugar

solution and they will wait 5 minutes. Finally, the pH of the saliva is will be determined again.

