8.3 Exclusion criteria

- Children with systemic disorders who need special care and/or who have the intolerance to milk drinks or allergy to any of the components of the experimental and/or the placebo beverage.
- Children who don't like milk.
- Children with severe decay

8.4 Lifestyle consideration:

The children's parent will inform when:

- The child uses antibiotic
- The child visits another dentist and the dentist use Fluor.
- The child uses an antiseptic or mouthwash.
- The child improves the brush frequency.

9 Study intervention

Primary Outcome Measure:

1. Change in remineralization of tooth decay

DIAGNOdent peak reading in three moments, at the beginning and at the end of the milk without probiotic (after 3 months), and at the end of the milk with probiotic (after 3 months) (Table 1).

Secondary Outcome Measures:

1. Change of salivary pH after a rinse with sugar.

Change pH after a rinse with sugar (point of difference), in three moments, at the beginning and at the end of the milk without probiotic (after 3 months), and at the end of the milk with probiotic (after 3 months) (Table 1).

2. Change of Dental Plaque Index

Silness-Löe plaque index in three moments, at the beginning and at the end of the milk without probiotic (after 3 months), and at the end of the milk with probiotic (after 3 months) (Table 1).

3. Change of concentration of group mutans streptococci in saliva

Colony Forming Units (CFUs) determination in three moments, at the beginning and at the end of the milk without probiotic (after 3 months), and at the end of the milk with probiotic (Table 1).

TABLE 1.

Variable	Scale of measurement	Data	Type of variable	Measure Type	Measure of dispersion
BEFORE (Control and Intervention)					
Diagnodent measurement	Quantitative	Values 0-99	Dependent	-Mean -Median	-Standard deviation -Inter-Quartile range
Change of salivary pH after a rinse with sugar.	Quantitative	Point of difference	Dependent	-Mean -Median	-Standard deviation -Inter-Quartile range
Dental Plaque Index	Qualitative	0=absent 1=present	Dependent	Frequency	NA
Colony Forming Units of the group mutans streptococci	Quantitative	UFC	Dependent	-Mean -Median	-Standard deviation -Inter-Quartile range
AFTER (Control and Intervention)					
Diagnodent measurement	Quantitative	Values 0-99	Dependent	-Mean -Median	-Standard deviation -Inter-Quartile range

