Change of salivary pH after a rinse with sugar.	Quantitative	Point of difference	Dependent	-Mean -Median	-Standard deviation -Inter-Quartile range
Dental Plaque Index	Qualitative	0=absent 1=present	Dependent	Frequency	NA
Colony Forming Units of the group mutans streptococci	Quantitative	UFC	Dependent	-Mean -Median	-Standard deviation -Inter-Quartile range

10 Statistical considerations

Statistical hypothesis

Primary Efficacy

H01: There is no significant difference of consumption of commercial milk beverages enriched with *Lactobacillus rhamnosus* and *Bifidobacterium longum* in diagnodent measurement in comparison with commercial milk without probiotic.

Secondary Efficacy

H02: There is no significant difference of consumption of commercial milk beverages enriched with *Lactobacillus rhamnosus* and *Bifidobacterium longum* in change of pH of saliva before and after a rinse with sugar, in comparison with commercial milk without probiotic.

H03: There is no significant difference of consumption of commercial milk beverages enriched with *Lactobacillus rhamnosus* and *Bifidobacterium longum* in concentration of group mutans streptococci in saliva in comparison with commercial milk without probiotic.

H04: There is no significant difference of consumption of commercial milk beverages enriched with *Lactobacillus rhamnosus* and *Bifidobacterium longum* in dental plaque index in comparison with commercial milk without probiotic.

11 Statistical analysis

Data will be organized with Microsoft Excel. The analyses will be performed using the program SPSS® Statistics 25.0 version. Univariate descriptive

analyses: means, standard deviations, medians, and interquartile ranges according to the normality. Data comparisons will be performed with Students t-test for related samples. A p-value <0.05 was considered as statistically significant. If there are not data normally distributed, the comparison will be with Wilcoxon test. In the case qualitative variable (Dental plaque index), the comparison will be with McNemar's test.

11. Regulatory, ethical, and study oversight consideration

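### Plaque is hypothesised to fall, but coding it present/absent and using McNemar's test ignores most reductions; one quantitative value per child would be more efficient

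*Combined protocol and SAP*

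**What the plan says.** The outcome is a matter of amount. Hypothesis 4 in 7.1 is that the probiotic milk will "reduce the dental plaque", and the second secondary outcome in section 9 is the "Silness-Löe plaque index in three moments": baseline, end of the milk without probiotic, and end of the milk with probiotic. The measurement steps (7.7, step 3.4, and step 6.1 after each milk) only name the instrument: "Index dental plaque Sillness and Löe".

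Both blocks of Table 1 then class plaque as qualitative, coded "0=absent 1=present" and summarised as a frequency. Section 11, Statistical analysis, follows from that: "In the case qualitative variable (Dental plaque index), the comparison will be with McNemar's test". The other three outcomes are quantitative and get a paired t-test, or a Wilcoxon test if not normally distributed.

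The comparison of interest is given in section 7, Objectives and Endpoints: "The comparison of dental plaque index during the intake of milk without probiotic versus during the intake of milk with probiotic". H04 in section 10 contrasts the same two milks. No section gives the teeth or surfaces scored, the grades of the index, how a score becomes absent or present, or whether the 0/1 value belongs to a child, a tooth or a surface. The sample is one of convenience, with no number stated.

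**The concern.** McNemar's test uses only children who change category. If any plaque counts as present, a child who goes from heavy to light plaque is a tie and drops out of the test. The hypothesis predicts that kind of change, and where most children have some plaque it is the change most likely to occur. A real reduction could then be reported as no difference, although the examination had gathered the information needed to see it.

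A second, smaller matter is that the unit is unstated. If surfaces were entered as separate pairs, McNemar's test would treat surfaces in one mouth as independent.

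**Working it through.** The plan states no power or sample size for plaque, so there is no figure to reproduce. From the documents come the test, the 0/1 coding, the pairing within child and the 0.05 level (taken as two-sided). Everything else below is assumed.

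**Minimum for significance.** With k children changing category, all in the same direction, the exact two-sided p-value is 2 × 0.5^k. For k = 5 it is 0.0625; for k = 6 it is 0.031. At least six children must change category.

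**Power, one value per child.** Assume child scores with mean 1.0 and SD 0.5 at each visit, correlation 0.5 and a reduction of 0.25.

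- Paired t-test: SD of the difference = √(2 × 0.5² × (1 − 0.5)) = 0.5. With n = 40 the noncentrality is (0.25 / 0.5) × √40 = 3.16, giving 87% power. Simulation with scores held to an assumed 0–3 range gives 86%; Wilcoxon gives 84%.
- Exact McNemar with cut-off c: z1 = (c − 1.0)/0.5 and z2 = (c − 0.75)/0.5. The probability of improving is p10 = Φ(z2) − Φ2(z1, z2; 0.5), and of worsening p01 = Φ(z1) − Φ2(z1, z2; 0.5), where Φ2 is the bivariate normal probability. Power is the sum over k of Bin(k; n, p10 + p01) × P(exact p < 0.05 given k).

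| Cut-off | Present on control milk | p10 | p01 | Expected changers, n = 40 | Power, n = 40 | Power, n = 100 |
|---|---|---|---|---|---|---|
| 0 | 98% | 0.059 | 0.015 | 2.9 | 2% | 23% |
| 0.5 | 84% | 0.211 | 0.061 | 10.9 | 34% | 79% |
| 1.0 | 50% | 0.273 | 0.082 | 14.2 | 45% | 89% |
| Paired t | – | – | – | – | 86–87% | >99% |

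The uncorrected asymptotic McNemar does somewhat better at n = 40 (11%, 43%, 54%) but stays well below the t-test.

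**Sensitivity to effect size, n = 40.** For a reduction of 0.10 the t-test itself has only 23%, against 0%, 6% and 9% for exact McNemar at the three cut-offs. For 0.40 it has over 99%, against 17%, 81% and 85%.

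**Models less favourable to the t-test, n = 40, 12 surfaces per child.**

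| Model | Children with any plaque | t on mean grade | t on proportion of surfaces | Exact McNemar, any plaque |
|---|---|---|---|---|
| Surfaces graded 0–3 | 97% | 64% | 59% | 1% |
| | 81% | 53% | 54% | 14% |
| | 50% | 34% | 37% | 18% |
| Surfaces present/absent only | 99% | – | 75% | 0% |
| | 89% | – | 68% | 11% |
| | 60% | – | 43% | 17% |

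The proportion of surfaces keeps most of the gain without any grading.

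**Pooled surfaces, no true difference, n = 40.** Assume 60% of surfaces have plaque. Type I error of exact McNemar by within-child correlation of change:

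| Surfaces | 0 | 0.05 | 0.14 | 0.29 |
|---|---|---|---|---|
| 6 | 4% | 6% | 11% | 19% |
| 12 | 4% | 10% | 20% | 31% |

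The child-level t-test stays at about 5% throughout. A separate logistic model gave 5–12% with 6 surfaces and 5–23% with 12, as the child-by-period SD rose from 0.3 to 1.0.

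**The case against.** The plan is coherent as written: a binary variable, a frequency, and the standard test for one paired binary value. Absent versus present has an ordinary meaning, so what is missing is an explicit mapping from index to 0/1, not any notion of a cut-off. The 0–3 grading used in part of the working is not in the documents. This is a convenience-sample pilot with no power claim. All of that stands, and it makes this a question of efficiency, not validity.

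A reader might infer three stronger things that the documents do not support.

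- *That type I error is inflated.* No section says surfaces will be pooled. Pooling would also inflate error only if changes correlate within a child; at zero correlation there is no inflation.
- *That the plaque test is underpowered.* No sample size is stated. With 100 children exact McNemar reaches 79–89% at the two less extreme cut-offs, and the 2% figure needs 98% of children to have plaque. Only the loss relative to a child-level score is shown.
- *That the visits compared are open, or scored under different conditions.* Section 11 names no pair, but the objectives table and H04 imply end of control milk versus end of probiotic milk. Baseline plaque is scored the day after step 3.2 ("Clinical assessment of demineralization with Diagnodent, after of dental prophylaxis"), whereas after each milk it is scored before prophylaxis (6.1, then 6.6). That difference does not touch the implied pair.

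Grading also leaves more room for examiner judgement than present/absent, and the study is unmasked. That is a real cost of the preferred score.

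**Conclusion.** The point holds as a minor, cheap improvement to a secondary outcome. The present/absent coding discards every reduction that does not take a child from some plaque to none. In every scenario tried, child-level McNemar had less power than a child-level quantitative value. In the main illustration the gap at n = 40 is about 86% against 2–45%; in the less favourable models it is 34–75% against 0–18%. These sizes rest on assumed numbers of children, prevalence, effect, correlation and grading, none of which the documents give. The unstated unit is a secondary caution only.

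**What to change.** - In both blocks of Table 1, make plaque one quantitative value per child: the mean index score over a fixed set of teeth and surfaces, the same set at each visit. If only presence is recorded, use the child's proportion of those surfaces with plaque. Summarise by mean and SD, or median and interquartile range.
- In section 11, Statistical analysis, compare end of probiotic milk with end of control milk by the paired t-test or Wilcoxon test already planned.
- Keep present/absent as a descriptive frequency per child, with the rule for present stated in advance.

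The cost is one table row in each block, one sentence in section 11 and a short scoring definition. Scores must be recorded by surface at examinations already scheduled; grades cannot be recovered later if only 0/1 is written down. The regulatory and ethics section assigns the examination to an expert, but calibration is stated only for ICDAS (step 3.3: "dentist with calibration in ICDAS take this measure"). Without masking, the plaque criteria should be fixed and the examiner calibrated for plaque too. The change does not remove the confounding of milk with period, since all children take the milks in the same order.
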